Official Title: Implementation of Mandatory Hiataloplasty in
Sleeve Gastrectomy: Strategy for Gastro-Esophageal Reflux
Disease (GERD) Risk Reduction. Implementation of

NCT number: not available

Date: 03/11/2024

Abstract.

Background. Limited research supports hiatal hernia repair and reduced acid production as protective factors. Despite the scarcity of direct evidence, the multifactorial nature of postoperative GERD underscores the potential significance of hiatalplasty in preventing complications. The inclusion of mandatory hiatalplasty in gastric sleeve protocols is considered a promising advancement for improving patient outcomes and reducing long-term complications.

Objective. This study aims to assess the effectiveness of mandatory hiatalplasty during gastric sleeve surgery in decreasing postoperative GERD incidence in patients at a specialized bariatric surgery hospital in Tijuana, Baja California.

Methodology. This is a retrospective case series study based on clinical records of patients who underwent some type of bariatric surgery in hospital centers specialized in bariatric and high volume surgery in the city of Tijuana, Baja California, Mexico, from March to June 2022. The following information of interest will be obtained: age, sex, comorbidities, BMI, surgery performed, surgical time, intra and postoperative complications. Once the data capture process has been completed, a descriptive analysis will be performed with the SPSS statistical program in version 26 for MacOS. Means and standard deviation will be obtained for quantitative variables as well as frequencies and percentages for qualitative variables.

Key words. Incidence, Complications, Bariatric surgery, Obesity.

THEORETICAL FRAMEWORK

Obesity is a worldwide epidemic that has been developing over the last decades and represents one of the main public health problems today due to the numerous related comorbidities.

According to the World Health Organization (WHO), 13% of all adults in the world (approximately 650 million) suffer from some degree of overweight or obesity (1). The future scenario is not very encouraging since the WHO also reports that more than 350 million non-adult people suffer from this same condition, in addition, obesity worldwide has had an unexpected increase during the last 30 years; being that the prevalence of obesity and overweight increased up to 40% in some developed countries (1).

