Vertical gastrectomy or popularly known as gastric sleeve can lead to a weight loss of up to 30% of body weight in the first postoperative year, with a smaller weight loss for up to 5 years (37).

In addition to the restrictive effect that results from removing a portion of the stomach, there are other mediators that are related to satiety and hypocaloric effects such as GLP-1 and Peptide YY (PYY) (38) as well as ghrelin, an orexigenic hormone that significantly reduces its levels due to the reduction of ghrelin secreting cells P-D1 that are found mostly in the gastric fundus (39). Also, gastric sleeve has effects on the microbiota that are believed to be related to weight loss through a reduction in caloric energy absorption (40).

The gastric sleeve has been shown to have the greatest improvement in metabolic risk compared to any other bariatric procedure (41-43). The metabolic risk markers that have benefited the most are: reduction of blood pressure, glycosylated hemoglobin and inflammatory markers, among others that have not yet been fully studied (44).

COMPLICATIONS ASSOCIATED WITH SLEEVE GASTRECTOMY

Bariatric surgery has become for many the best method to treat obesity, especially in severe cases and due to the multiple benefits obtained after this type of procedure; however, as with any major surgery, there is a risk of complications, and although in the bariatric field they are relatively uncommon, when they occur they may require a multidisciplinary management that is not simple (45).

Sleeve gastrectomy, as a leading technique in metabolic and bariatric surgery, has gained popularity for its effectiveness in achieving considerable weight loss in a short period of time. However, this procedure is not without complications. The most common complications include bleeding, nutritional deficiencies and leakage (46).

One of the most prominent chronic complications of gastric sleeve is the development of postoperative de novo gastroesophageal reflux disease (GERD),

which can range from esophagitis to more serious conditions such as Barrett's esophagus and esophageal cancer (47). The prevalence of GERD in the Western population is estimated at 7.7%, and its pathogenesis is multifactorial, involving factors such as hypotonia of the lower esophageal sphincter (LES), inadequate transient relaxations of the LES, and the contribution of hiatal hernia (48).

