The incidence of postoperative GERD in patients undergoing gastric sleeve surgery is a growing concern. The prevalence of GERD in the general population is considerable, and its occurrence or exacerbation after bariatric surgery represents a significant clinical problem. Moreover, the management of postoperative GERD involves additional costs for both the patient and the health care system, in terms of long-term medication, clinical follow-up and, in some cases, surgical reintervention. The complexity of this problem lies in the multifactorial nature of its etiology. Factors such as hypotonia of the lower esophageal sphincter and the presence of hiatal hernia contribute to the development of GERD. Therefore, it is imperative to explore surgical strategies that can mitigate this risk. One such strategy is mandatory hiataloplasty during sleeve gastrectomy, which, although not extensively investigated in this specific setting, has the potential to address one of the key etiologic factors of postoperative GERD.

However, the adoption of mandatory gastric sleeve hiataloplasty presents not only technical challenges, but also involves considerations of surgeon training, hospital resources, and acceptance of new surgical protocols. The need for a more preventive and comprehensive approach to bariatric surgery is clear, but requires a solid evidence base and adaptation of current surgical practices. This context raises a significant issue: should mandatory hiataloplasty be integrated into the gastric sleeve to reduce the incidence of postoperative GERD and improve long-term outcomes for patients undergoing bariatric surgery?

HYPOTHESIS

Alternative hypothesis

Mandatory hiatal hernia repair performed during gastric sleeve surgery significantly reduces the incidence of postoperative gastroesophageal reflux disease (GERD) compared to gastric sleeve performed without mandatory hiatal hernia repair.

Null hypothesis

Mandatory hiatal hernia repair performed during gastric sleeve surgery does not have a significant impact on reducing the incidence of postoperative gastroesophageal reflux disease (GERD) compared to gastric sleeve performed without mandatory hiatal hernia repair.

OBJECTIVES

General

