To evaluate the efficacy of mandatory hiatal hernia repair (hiatoplasty) performed during gastric sleeve surgery in reducing the incidence of postoperative gastroesophageal reflux disease (GERD) in patients undergoing this procedure in a hospital specializing in bariatric surgery in Tijuana, Baja California.

Specific

Demographic characteristics and comorbidities in patients undergoing gastric sleeve with hiatoplasty: These patients usually have significant obesity, often accompanied by comorbidities such as type 2 diabetes, hypertension, sleep apnea, and gastroesophageal reflux disease (GERD). Demographic characteristics may vary, but the prevalence of obesity and its associated comorbidities is high in many regions, including Tijuana, Baja California.

Incidence of postoperative GERD in patients undergoing gastric sleeve with mandatory hiatoplasty: Hiatal hernia repair is often performed to reduce the risk of postoperative GERD by repairing a herniated hiatus during gastric sleeve surgery. However, the exact incidence of postoperative GERD can vary and depends on factors such as surgical technique, patient anatomy and postoperative management.

Comparison of postoperative complication rates, including GERD: Postoperative complications may include, but are not limited to, bleeding, infection, sleeve stenosis, and GERD recurrence. Comparison of complication rates between patients with and without mandatory hiatal hernia repair may provide insight into the effectiveness of this technique in mitigating specific risks.

Postoperative quality of life analysis: Postoperative quality of life can be significantly improved after bariatric surgery due to weight loss and improvement of comorbidities. Specific measures may include, but are not limited to, physical mobility, self-esteem, relief of symptoms of comorbidities, and overall satisfaction with the results of surgery.

Evaluation of the safety and technical feasibility of mandatory hiatoplasty: The integration of hiatal hernia repair into gastric sleeve surgery should be evaluated in terms of technical feasibility, safety, and effectiveness in preventing recurrence of hiatal hernias and GERD. This may involve analysis of complication rates, specific surgical techniques, and long-term.

MATERIALS AND METHODS

Research design

A retrospective case series will be performed.

Universe of study

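### The hypotheses compare sleeve gastrectomy with and without mandatory hiatal repair, but only sleeves with hiataloplasty can enter, so no reduction in GERD can be tested or estimated

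*Protocol*

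**What the plan says.** **Aims (Protocol).** Under HYPOTHESIS, the alternative is that mandatory repair "significantly reduces the incidence of postoperative gastroesophageal reflux disease (GERD) compared to gastric sleeve performed without mandatory hiatal hernia repair". The null is that it "does not have a significant impact on reducing the incidence of postoperative gastroesophageal reflux disease (GERD) compared to gastric sleeve" done without mandatory repair. The research question asks: "should mandatory hiataloplasty be integrated into the gastric sleeve to reduce the incidence of postoperative GERD". The abstract sets out to "assess the effectiveness of mandatory hiatalplasty during gastric sleeve surgery in decreasing postoperative GERD incidence", and the general objective is "To evaluate the efficacy of mandatory hiatal hernia repair (hiatoplasty) performed during gastric sleeve surgery in reducing the incidence" of postoperative GERD. One specific objective is headed as a comparison and says: "Comparison of complication rates between patients with and without mandatory hiatal hernia repair may provide insight into the effectiveness of this technique". Another specific objective, on safety and feasibility, includes effectiveness against recurrence of hiatal hernia and GERD.

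**Methods (Protocol).** The design is a retrospective case series. Universe of study and Inclusion criteria both require a gastric sleeve with hiataloplasty, and step 2 of Description of the study reviews only records that meet those criteria. The sample size uses the formula for a single prevalence. STATISTICAL ANALYSIS gives frequencies and percentages, with means or medians for quantitative variables.

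**The concern.** The aims need two groups and the eligibility rules supply one. The words *reduces* and *compared to* require a GERD frequency in patients operated on without mandatory repair, and the protocol excludes those of them who had no repair at all.

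What is at stake is the conclusion. The protocol asks whether mandatory hiataloplasty should become part of the operation, and its Significance section speaks of a possible new standard. If the report answers in the words of the hypothesis, a recommendation to change practice would rest on an uncontrolled percentage. A low GERD frequency could reflect patient selection, the sleeve technique, short or incomplete follow-up, or the way GERD was recorded, and nothing in the design would separate these from the repair.

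**Working it through.** No effect size has to be computed. The check sets what the aims require against what the methods provide.

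**1. Who belongs in the comparator.** Sleeve without mandatory repair covers two kinds of patient: (a) those with no repair, and (b) those repaired selectively, at the surgeon's choice.

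**2. Who can enter.**

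| Patient | Needed by the hypotheses | Admitted by universe, inclusion criterion and step 2 |
|---|---|---|
| Sleeve, mandatory repair | yes | yes |
| Sleeve, selective repair | yes, as comparator (b) | yes, but not identifiable (step 3 below) |
| Sleeve, no repair | yes, as comparator (a) | no, n = 0 |

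**3. Can group (b) be identified?** The variable table defines eight variables: age, sex, chronic comorbidities, BMI, obesity level, duration of surgery, trans-operative complications and postoperative complications. None records whether a repair was mandatory or selective. Step 3 of the study description adds the type of procedure and bleeding, but not this distinction. On Appendix 1 the nearest items are a gap-closure box, which does not say which gap, and a free-text entry for other surgery. Neither is defined for this purpose. Even if group (b) could be found, the contrast would be repaired against repaired.

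**4. Is there an outside reference?** None is named. The only GERD rate given is background: "The prevalence of GERD in the Western population is estimated at 7.7" per cent. That is a population prevalence, not a rate after sleeve. The p = 20% in the sample-size section is tied to no outcome or group.

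**5. What the sample size is for.** The formula is n = Z² × p × q / d².

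- With Z = 1.96, p = 0.20, q = 0.80 and d = 0.05: 3.8416 × 0.16 / 0.0025 = 245.9, so 246.
- With the printed q = 70%: 3.8416 × 0.14 / 0.0025 = 215.1, so 216.
- With a margin of 10%: 61.5 (q = 0.80) or 53.8 (q = 0.70).

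None of these gives the stated 275. That is a separate fault and this point does not depend on it. What matters here is that the formula has one proportion, and no second rate, difference or power. At n = 275 and p = 20% the half-width is 1.96 × √(0.16 / 275) = 4.7 percentage points, which is the precision of one group's percentage.

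**6. Do the data support a single-group aim?**

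- Baseline GERD is on Appendix 1 (personal history) and is a listed comorbidity.
- Postoperative GERD is a category of the postoperative complications variable.
- The Appendix 2 Reflux Scale asks about current symptoms and does not depend on a baseline condition.
- The Appendix 2 row on change in reflux offers only aggravated, unchanged, improved or resolved, and patients without conditions skip the question. It has no category for new reflux.
- Hiatal hernia recurrence has no postoperative item. The Appendix 1 hernia box belongs to the preoperative examination, its endoscopy item is under previous studies, and Appendix 2 has no hernia item.

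**The case against.** **Selective repair as the comparator.** Read literally, a patient repaired by choice is without mandatory repair and could enter. This stands as a reading of the words, but it does not rescue the comparison: those patients cannot be identified, and the unrepaired part of the comparator stays out.

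**The abstract is broader.** It describes a "retrospective case series study based on clinical records of patients who underwent some type of bariatric surgery", and Appendix 1 lists other operations. But the abstract defines no comparator, the Methods criteria are narrower, and other bariatric operations are not sleeves without repair.

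**The analysis plan may deal with it.** It could add a test or an interval. It could not add patients whom the eligibility criteria exclude.

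**The wording is soft in places.** The comparison objective says only that it may give insight, and the title states a motivation. Both are fair, and the title can stay. The hypotheses are not soft.

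**A reader might infer that the study has no usable aim.** The protocol does not support that. Its specific objectives already include the incidence of postoperative GERD after sleeve with mandatory hiatoplasty, and the methods suit that aim.

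**A reader might also want a figure for the effect that is missed.** The protocol gives no share of selective repairs, no GERD rate without mandatory repair and no expected effect. Any such figure would only return its own assumptions.

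**Conclusion.** The contradiction is real and must be fixed. As written, neither hypothesis can be tested and no reduction in GERD relative to sleeve without mandatory repair can be estimated. Its size is structural: the protocol admits no unrepaired sleeves, defines no item that separates mandatory from selective repair, and names no external control. This rests on the eligibility wording alone and on no assumed rate. It does not extend to the single-group incidence objective, which remains sound as a descriptive aim.

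**What to change.** Change the wording as follows.

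1. Delete both hypotheses. Promote the existing incidence objective to general objective: *To estimate, with 95% CI, the incidence of postoperative GERD after sleeve gastrectomy with hiataloplasty*, reported separately for patients without and with GERD at baseline (Appendix 1).
2. Take postoperative GERD from the postoperative complications variable, supported by the Reflux Scale. Use the Appendix 2 reflux-change row only for patients with baseline GERD.
3. Reword the comparison objective: *To describe postoperative complication rates, including GERD, after sleeve with hiataloplasty*.
4. In the safety and feasibility objective, remove the clause on effectiveness against recurrence, and drop hiatal hernia recurrence because no postoperative item records it.
5. Remove the efficacy and effectiveness wording from the abstract objective and the general objective, and limit the conclusion to single-group estimates. The title need not change.

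**Cost.** No new data are needed. The claim becomes descriptive, and the subgroup estimates are less precise than the overall one. As an illustration, assume that 10% to 50% of 275 patients have baseline GERD, that follow-up is complete, that new GERD is near 20%, and that persistence is near 50% (the widest case). The Wilson 95% intervals are then:

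| Baseline GERD (assumed) | New GERD, no baseline GERD | Persistent GERD, baseline GERD |
|---|---|---|
| 10% | 49/247: 15.3% to 25.3% | 14/28: 32.6% to 67.4% |
| 50% | 27/137: 13.9% to 27.2% | 69/138: 41.8% to 58.2% |

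Incomplete follow-up would widen them.

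Keeping the comparison would mean admitting sleeves without mandatory repair, with a two-group sample size and an adjusted analysis. That is a redesign and not part of this fix.

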Electronic clinical records of patients over 18 years of age of indistinct gender who underwent gastric sleeve with hiataloplasty for obesity or overweight management in a hospital center specialized in bariatric surgery in Tijuana, Baja California.

Study period

March 2024 - July 2024.

Sample size

To calculate the sample size, the formula for prevalence studies for infinite populations was used, considering a confidence interval of 95% and a margin of error of 5%. The formula is presented below:

$$n = \frac{Z_{\alpha/2}^2 (p * q)}{d^2}$$

where,

$Z_{\alpha/2}$ = Z-score of a normal distribution $\alpha/2 = 1.96$

$p = 20\%$

$q = 100 - p = 70\%$.

d^2 = margin of error = 10

n= a minimum of 275 patients is required

Sampling

Non-probabilistic sampling will be used.

Inclusion and non-inclusion criteria

Inclusion criteria

- Patients over 18 years of age.
- Gender indistinct.
- Overweight, obesity grade I, II, III, super obesity or super-super obesity.

- Underwent gastric sleeve with hiataloplasty for obesity management at a high volume Tijuana hospital dedicated to bariatric surgery.

Non-inclusion criteria

- Patient records with incomplete information.

Description of the study

1. This study will be subject to review by the Research and Research Bioethics Committees of the hospital in question. Since this is a retrospective study, informed consent is not required.
2. After approval, the electronic clinical records of overweight and obese patients who meet the inclusion criteria and who underwent bariatric surgery for obesity management in Tijuana during the study period will be reviewed.
3. The following information of interest will be obtained from the file: age, sex, comorbidities, BMI, type of procedure, duration of surgery, final bleeding, immediate postoperative and transoperative complications. Patient follow-up information will also be obtained, which is obtained both in person for patients who can attend follow-up consultations and remotely by e-mail after sending a medical questionnaire and subsequent response from patients who reside in another city or country and therefore cannot attend their follow-up consultations in person.
4. Finally, the data will be captured in SPSS for statistical analysis.
5. To measure the quality of life of patients and the effectiveness of surgery, the Bariatric Analysis and Reporting Outcome System (BAROS) scale will be used.

Definition and operationalization of the study variables

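### The sample size of 275 does not follow from the printed formula and inputs: q is given as 70% beside p = 20%, and the margin is both 5% and 10

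*Protocol*

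**What the plan says.** In the protocol, Materials and Methods, the Sample size section says that "the formula for prevalence studies for infinite populations was used", "considering a confidence interval of 95% and a margin of error of 5" per cent. The formula is printed as n = Z²(p × q)/d², with Z and d both squared. The legend below it lists Z = 1.96, p = 20% and q, defined as 100 − p, equal to 70%. It then has "d^2 = margin of error = 10". The conclusion is "n= a minimum of 275 patients is required".

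The section does not say which outcome p = 20% describes and gives no source for it. It states no allowance for unusable records and no finite-population correction. The only GERD frequency in the document is in the section on complications of sleeve gastrectomy: "The prevalence of GERD in the Western population is estimated at 7.7" per cent.

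**The concern.** Two contradictions are visible without any modelling. First, q is defined as the complement of p, yet 20% and 70% do not add to 100%, so one of the two is wrong. Second, the margin of error is 5% in the prose and 10 in the legend, and the legend equates the margin with its own square. Neither reading of the legend fits the prose: d = 5 gives d² = 25, and d = 10 gives d² = 100.

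The figure of 275 is the study's only planning number and is called a minimum. The Statistical Analysis section plans descriptive summaries only, so precision is all that this calculation can justify. If the figure cannot be traced to its inputs, the precision it is meant to secure is uncertain. Whether 275 meets the 5-point margin depends on which of p and q is the misprint.

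**Working it through.** **Inputs**, all from the Sample size section: Z = 1.96; p = 20%; q = 70% as printed, or 80% as the complement of p; margin 5% (prose) or 10 (legend, labelled d²). If q = 70% is the correct entry, p would be 30%, so that case is included.

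**Attempt to reproduce 275** with n = Z²pq/d², Z² = 3.8416, rounding up:

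| p | q | d | Calculation | n |
|---|---|---|---|---|
| 20% | 80% | 5% | 3.8416 × 0.20 × 0.80 / 0.0025 = 245.86 | 246 |
| 20% | 70% | 5% | 3.8416 × 0.20 × 0.70 / 0.0025 = 215.13 | 216 |
| 30% | 70% | 5% | 3.8416 × 0.30 × 0.70 / 0.0025 = 322.69 | 323 |
| 20% | 80% | 10% | 3.8416 × 0.20 × 0.80 / 0.01 = 61.47 | 62 |
| 20% | 70% | 10% | 3.8416 × 0.20 × 0.70 / 0.01 = 53.78 | 54 |
| 30% | 70% | 10% | 3.8416 × 0.30 × 0.70 / 0.01 = 80.67 | 81 |
| 20 | 70 | d² = 10 | 3.8416 × 20 × 70 / 10 = 537.82 | 538 |

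The last row takes the legend literally, in percentage points. It implies a margin of √10 ≈ 3.2 points, which the protocol states nowhere. It tests the printed arithmetic and is not a required sample size.

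None of these is 275. Confidence levels of 90% and 99% and a one-sided Z of 1.645 do not give it either. A continuity correction at p = 20%, q = 80%, d = 5% gives 266.

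**What does match.** With the printed values and Z not squared, 1.96 × 20 × 70 / 10 = 274.4, which rounds up to 275. The same slip with q = 80 gives 1.96 × 20 × 80 / 10 = 313.6. With p = 30 and q = 70 it gives 1.96 × 30 × 70 / 10 = 411.6. The printed 20, 70 and 10 are therefore very likely the numbers used. This also makes a text-extraction error an unlikely explanation.

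**Precision**, as the 95% half-width 1.96 × √(p(1 − p)/n):

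- n = 275, p = 20%: 1.96 × √(0.16/275) = 4.73 points
- n = 275, p = 30%: 1.96 × √(0.21/275) = 5.42 points
- n = 246, p = 20%: 1.96 × √(0.16/246) = 5.00 points
- n = 323, p = 30%: 1.96 × √(0.21/323) = 5.00 points

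**The case against.** The strongest reply is that the error does little harm. With the stated p = 20% and the 5% margin in the prose, the minimum is 246, so 275 exceeds it. If the legend's 10 is the intended margin, 62 records would do (81 at p = 30%). A shortfall against a margin stated as such arises only if p = 30% was meant, and then the half-width is 5.4 points instead of 5. The study reviews existing records and is descriptive. All of this stands and limits how much weight the point deserves.

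It is also fair that the document does not say how 275 arose. The unsquared Z is inferred from an exact match. An unstated inflation also comes close: 246/0.9 = 273.3 (274), 246 × 1.1 = 270.6 (271) or 216/0.8 = 270. None gives 275, however, and the section states no such allowance.

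The 7.7% figure is a population prevalence, not a postoperative frequency, so it does not show 20% to be wrong. It shows only that the document offers no basis for 20%.

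None of these replies removes the two contradictions or makes the printed formula return 275.

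**Conclusion.** The concern holds. As written, the derivation is wrong: q is not the complement of p, two incompatible margins are given, and the formula does not yield 275 from any combination of the printed inputs. The probable origin is three slips together (Z not squared, q = 70, and 10 used as d²), though this is inference.

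The consequence is modest. If p = 20% is right, 275 analysed records give ±4.7 points and meet the 5-point margin with 29 records to spare (275 − 246). If p = 30% was meant, they give ±5.4 points and fall 48 short of the 323 needed (323 − 275). These half-widths rest on the normal approximation that the formula itself uses, and on 275 being the number analysed. The fault is an untraceable and self-contradictory calculation, not a clearly undersized study. It should be corrected.

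**What to change.** Rewrite the Sample size section as follows.

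- State which outcome p describes, its value and its basis.
- Set q = 1 − p.
- Give one margin d (5%, as in the prose) and remove the legend entry that equates d² with the margin.
- Square both Z and d, and restate n. With p = 20% and d = 5% the minimum is 246.
- If 275 records are analysed, give the precision as ±4.7 points at p = 20%. If p = 30% was meant, restate the margin as ±5.4 points.

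The figure of 275 should not be explained afterwards as 246 plus an allowance for unusable records. The protocol states no allowance, and about 246 usable records would give ±5.0 points, not ±4.7.

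The cost is protocol wording only. No records are added if p = 20%, or if p = 30% with the margin restated. Holding a 5-point margin at p = 30% would need 323 records, 48 more. The Schedule of activities marks execution as completed and data analysis as pending, so extra records may no longer be practical. The precision can still be corrected before results are reported, using the number of records actually analysed.

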APPENDIX 1. DATA COLLECTION FORM

"Implementation of Mandatory Hiataloplasty in Sleeve Gastrectomy: Strategy for Gastro-Esophageal Reflux Disease (GERD) Risk Reduction."

Identification sheet

ID: _____ **Fecha:** _____
Name: _____ **Gender:** : M F Other **Age:** _____
 years.
Teléfono: _____ **Email:** _____
Marital Status: Single Married Divorced Common-law
Country of residence: Mexico USA Other: _____
Nationality: Mexico USA Other: _____
Occupation: _____
Attending Physician: [name] [name]: _____
Planned Surgery: Sleeve Y-Roux SADIS/SD Mini-Gastric Bypass (MGB)
 Rev Sleeve Band Rev Bypass Other: _____
Planned surgery date: _____
Size: _____ meters **Weight:** _____ (before diet): _____ kg **IMC:** _____ : _____
HR: _____ bpm **FR:** _____ rpm **BP:** _____ mmHg **T:** _____ °C

Background

Allergies: Denied Penicillin Sulfonamides AAS

Otro: _____

Smoking: Denied Active Inactive Inactive time (years): _____

Cigarettes per week: _____

Years: _____

Alcoholism: Denied Active Inactive

Social / Drinks per week: _____

Years: _____

Toxicomania: Denied Active Inactive

Type of drug used: Marijuana Cocaine Ecstasy LSD

Heroin Fentanyl Other: _____ Years: _____

Previous hospitalizations: denied Yes How long ago? _____

Motivo:

Blood type: A B AB O

Previous transfusions: denied Yes How long ago? _____

Motivo:

Heredofamiliares

Diabetes: Denied Father Mother Grandparents Siblings Children

Hypertension: Denied Father Mother Grandparents Siblings Children

Cardiac: Denied Father Mother Grandparents Siblings Sons Sons.

Cancer: Denied Father Mother Grandparents Siblings Children Psychiatric: Denied

Father Mother Grandparents Siblings Children Endocrine: Denied Father Mother

Grandparents Siblings Children

Personal

Diabetes: No Yes Time of evolution: _____ years Are you in control? No Yes

Treatment used:

No treatment Insulin: _____ IU/day.

Metformin: _____ mg/day Hypoglycemic: _____

Other: _____

Arterial Hypertension: No Yes **Time of evolution:** _____ years **Is it under control?** No Yes

Treatment used:

 No treatment	 ACEI: _____
 ARA 2: _____	 BetaBlocker: _____
 Ca Antagonist: _____	 Diuretic: _____

Other Cardiovascular Diseases: No Yes

Enfermedad(es): _____

Time of evolution: _____ years

Treatment used: _____

Cancer: No Yes In recurrence

Type of cancer: _____

Time of evolution: _____ years

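### Selecting patients on having received hiataloplasty leaves the completion side of the feasibility objective unanswerable and restricts complication and GERD rates to recipients of the repair

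*Protocol*

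**What the plan says.** The Universe of study section takes records of adults "who underwent gastric sleeve with hiataloplasty for obesity or overweight management in a hospital center specialized in bariatric surgery". The Inclusion criteria repeat the condition: "Underwent gastric sleeve with hiataloplasty for obesity management at a high volume Tijuana hospital dedicated to bariatric surgery". Step 2 of the Description of the study applies these criteria when records are pulled. Research design states "A retrospective case series will be performed".

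Among the specific objectives is "Evaluation of the safety and technical feasibility of mandatory hiatoplasty". On how this will be judged, the protocol offers only an unfinished sentence: "This may involve analysis of complication rates, specific surgical techniques, and long-term".

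In Appendix 1 the planned-operation field begins "Planned Surgery: Sleeve Y-Roux SADIS/SD Mini-Gastric Bypass (MGB" and goes on to other bariatric procedures. The field for the operation performed has the same kind of list. Neither has an entry for hiataloplasty. The table of study variables has no item for a repair omitted or abandoned.

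**The concern.** The subject of the study is a policy: repair as an obligatory part of the sleeve. Whether such a policy is technically feasible depends in part on how often the step can be carried out in the patients meant to receive it. A cohort defined by receipt of the step cannot show that.

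The same selection applies to the safety and GERD results. A difficult or complicated operation is a plausible reason for leaving the repair out. If such cases had worse outcomes, the recipients' figures would look better than those of everyone operated on under the policy, yet they would be used to support making the repair mandatory.

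This is separate from the absence of a no-repair comparator. Even as a single-arm description, the cohort lacks the denominator of intended repairs, and adding a control group of sleeves without repair would not supply it.

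**Working it through.** **1. Can the omitted cases enter by another route?**

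- Universe of study and Inclusion criteria: both require receipt of hiataloplasty.
- Description of the study, step 2: applies those criteria again.
- Abstract: describes a wider group, "patients who underwent some type of bariatric surgery in hospital centers specialized in bariatric and high volume surgery". This conflicts with the Universe of study and does not override the criterion.
- Specific objectives: one item says "Comparison of complication rates between patients with and without mandatory hiatal hernia repair may provide insight", but patients without the repair cannot be included.
- Appendix 1 and the variable table: neither records whether hiataloplasty was planned, attempted, completed or omitted.

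Nothing restores the denominator.

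**2. The protocol's own figure.** The Sample size section states 275, from n = Z² × p × q / d². With Z = 1.96, p = 0.20, q = 0.70 as printed and d = 0.05, n = 215.13, or 216. With q = 0.80 (100 − 20), n = 245.86, or 246. With d = 0.10 the results are 54 and 62. None gives 275. That is a separate matter; 275 is used below only to set the scale.

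**3. Completion.** The completion proportion is repairs done divided by repairs intended. Under the criterion, numerator and denominator are the same patients, so it is 275/275 = 100% whatever happened in theatre. An exact 95% interval computed on that ratio would have a lower limit of 0.025^(1/275) = 98.7%, a precision with no information behind it.

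If c is the true completion proportion, intended operations = 275/c. The values of c are assumptions; the documents give none.

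| c | 275/c | unseen |
|---|---|---|
| 0.99 | 277.8 | 2.8 |
| 0.95 | 289.5 | 14.5 |
| 0.90 | 305.6 | 30.6 |

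**4. Complications.** The rate among all intended = c × r_in + (1 − c) × r_out, where r_in applies to recipients and r_out to the excluded. Take r_in = 5% (assumed) and vary r_out (assumed):

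| r_out | c = 0.99 | c = 0.95 | c = 0.90 |
|---|---|---|---|
| 2% | 4.97% | 4.85% | 4.70% |
| 5% | 5.00% | 5.00% | 5.00% |
| 10% | 5.05% | 5.25% | 5.50% |
| 20% | 5.15% | 5.75% | 6.50% |
| 30% | 5.25% | 6.25% | 7.50% |
| 50% | 5.45% | 7.25% | 9.50% |

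The error in the reported 5% is (1 − c) × (r_in − r_out). It is zero when the rates are equal, favourable when r_out is higher and unfavourable when r_out is lower. In this grid it runs from 0.3 points too high to 4.5 points too low.

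**5. GERD.** The same formula applies. Take 20% among recipients, borrowing the p of the sample-size formula (the protocol does not say what that p measures). Letting r_out run from 0% to 100% bounds the rate among all intended:

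- c = 0.99: 0.99 × 20% = 19.8%, to 19.8% + 1% = 20.8%
- c = 0.95: 19% to 24%
- c = 0.90: 18% to 28%

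**The case against.** Selecting by procedure received is usual in a retrospective descriptive case series, and feasibility is the last of five specific objectives. The protocol never names completion as its feasibility measure. It mentions complication rates and techniques, and operative time, bleeding, intraoperative events and reintervention all vary freely within the cohort. A reader might infer that the whole feasibility objective is settled at 100% in advance; the text does not support that. Only the completion component is fixed. This part of the objection stands. It does not remove the gap, because whether a mandatory step can be carried out is basic to its technical feasibility, and the complication rates that the protocol does name use the same restricted denominator.

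A reader might also infer that abandoned repairs are all excluded. The criterion turns on having undergone the repair, not on its completion. A repair started and then stopped could be charted as hiataloplasty, with the event captured among intraoperative complications. Exclusion is clear for omitted repairs and uncertain for abandoned ones.

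A third tempting inference is that the safety results are biased favourably as a matter of fact. The documents give no count, reason or complication rate for such cases, and an omitted repair may involve less dissection and fewer complications. Favourable bias is plausible, not shown.

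It could be said that the analysis plan may define the feasibility measure. It may, but it cannot recover records that the eligibility criterion keeps from being pulled.

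**Conclusion.** The point holds in this form: sleeves done under the mandatory policy without the repair fall outside the cohort, and possibly those with an abandoned repair as well. The completion component of technical feasibility cannot be estimated from this cohort. This follows from the wording of the criterion and needs no numerical assumption.

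Complication and GERD rates apply to recipients only. Their bias as estimates for the policy is unknown in direction and size. Under the assumed inputs it is negligible at 99% completion unless the excluded cases fare very differently, and reaches a few percentage points at 90% with a large difference. The documents do not say where in that range this hospital lies.

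The change is worth making because it is cheap and serves a stated objective. It ranks below the missing comparator for the hypothesis on GERD reduction.

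**What to change.** 1. Redefine the cohort as all consecutive sleeve gastrectomies scheduled under the mandatory-hiataloplasty policy within the surgery window, whether or not the repair was done. State the date from which the policy applied, and first reconcile the windows: the Abstract gives March to June 2022, the Study period March to July 2024.
2. Add one item to Appendix 1: repair planned, attempted, completed or omitted, with the reason when not completed. Define when a repair counts as completed.
3. Report the completion proportion with its interval, and complications and GERD, on that denominator. Give the received-repair subset as a secondary description.
4. Complete the unfinished sentence under the feasibility objective and name completion there.

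**Cost:** changed inclusion wording, a somewhat wider pull from the same electronic records, and one form field. The result depends on charts stating whether and why a repair was not done; where they do not, report the number with unknown status. The headline safety figure may turn out slightly less favourable.
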